We also considered pharmacotherapy comparisons. But many participants would be ineligible for use (e.g., medical condition) and, if disseminated, many people would face access barriers (e.g., medication affordability). Some medications (e.g., varenicline) require a physician visit and prescription. For Nicotine Replacement Therapy (NRT), adequately addressing side effects for a nationally-recruited sample who will have had no prior personal contact with the study would be problematic [74, 75].

Table 4. Participant surveys and time points when they will be administered. (All participants)

Measure	Screening	Baseline	3- month	6- month	12- month	Purpose
Eligibility & Enrollment (24 items)	x					Eligibility, Enrollment, & Stratification
Demographics (19 items)		x				Stratification & Exploratory
Nicotine Dependence (6 items)		x	x	x	x	Stratification & Aim 1
Smoking/Tobacco History (4 items)		x				Exploratory Aim
Tobacco Use (6 items)		x	x	x	x	Aim 1

Acceptance of cues (27 items)	x	x			Aim 2 & Exploratory
Quality of Life (8 items)	x	x			Exploratory Aim
Quality of Life (6 items)			x	x	Exploratory Aim
Panic Symptoms (5 items)	x	x	x	x	Exploratory Aim
PTSD Symptoms (6 items)	x	x	x	x	Exploratory Aim
Generalized Anxiety Symptoms (7 items)	x	x	x	x	Exploratory Aim
Social Anxiety Symptoms (17 items)	x	x	x	x	Exploratory Aim
Depression Symptoms (20 items)	x	x	x	x	Exploratory Aim
Distress Tolerance (6 items)	x	x			Exploratory Aim
Values (10 items)	x	x			Aim 2
Growth Mindset (6 items)	x	x			Exploratory Aim
Quitting Self-Efficacy (1 item)	x				Stratification
Alcohol Use (4 items)	x	x	x	x	Exploratory Aim
Mobile Device Use (8 items)	x				Exploratory Aim
Receptivity/utilization (14 items)		x			Acceptance/Adherence
Receptivity/utilization (2 items)			x	x	Acceptance/Adherence
Cessation & Extra Aids (5 items)		x	x	x	Aim 1 and Exploratory
Willingness to discuss (1 item)				x	Follow-up

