Aim 2: ACT Mediators. Acceptance of internal cues to smoke: Measured using the Avoidance and Inflexibility Scale (AIS; $\alpha = .93$; [16, 20], which assesses one's willingness to experience sensations (9 items), emotions (9 items), and thoughts (9 items) that cue smoking. A sample item for the sensations scale is: "To what degree did you allow yourself to have urges to smoke?" Commitment to quitting. Commitment to quitting despite internal (e.g., cravings, anxiety) and external (e.g., smoking in the social environment) cues to smoke will be measured using the Commitment to Quitting Scale (CQS; $\alpha = .93$; [59]). Sample item: "No matter how many people around me smoke, I won't let myself smoke once I quit." Regarding assessment timing, three months post randomization is when we expect acceptance and commitment to increase the most, as consistent with past ACT smoking cessation studies [16, 17, 20, 82], and would allow testing of our hypothesized model of increases in acceptance and commitment at three months mediating the impact of the intervention on smoking cessation by twelve months.

Aim 3: Costs of delivery, for cost-effectiveness analyses. Costs associated with each app's delivery include the cost to: (1) host the servers and databases, (2) conduct software updates to accommodate ongoing changes in operating systems, (3) have programming staff to answer technical questions, and (4) cost of facilities and equipment needed to maintain each (e.g., office space for personnel, computers). NCI, the host of QuitGuide, has agreed to provide these costs for QuitGuide [32]. Research-related costs will not be included.

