Exploratory aim: Moderators of treatment outcome. Hypothesized moderators of treatment effectiveness will be heaviness of smoking (smoking at least 20 cigarettes per day vs. less than 20 at baseline), acceptance of cravings to smoke (AIS scores below vs. above the median), mental health symptoms (positive vs. negative screen for depression, anxiety, or heavy alcohol use), and racial/ethnic minority status (Caucasian vs. minority). Mental health symptoms will be assessed as follows: (1) depression screening via the 10-item Center for Epidemiologic Studies Depression Scale (CES-D; cutoff ≥ 10) [83, 84]; (2) anxiety screening via the Generalized Anxiety Disorder Scale; (GAD-7; cutoff ≥ 10 , [85]); (3) alcohol screening via the Alcohol Use Disorders Identification Test—Consumption items (AUDIT-C; cutoffs ≥ 4 drinks/day for women, ≥ 5 drinks/day for men or 7 drinks/week for women, 14 drinks/week for men [86, 87]).

Treatment acceptability/adherence: Treatment satisfaction and utilization. Measured with the 8-item Treatment Satisfaction/Utilization Scale used in our pilot. Sample satisfaction item: "Overall, how satisfied are you with your assigned app?" Sample utilization items: "Overall, about how many times per week did you use the strategies taught in your assigned app?" and "How useful was your assigned app's quit plan?"

Cessation pharmacotherapy usage: Measures number of days per week, number of total weeks, and start/end dates, that participants on their own elected to use (1) nicotine replacement therapy (i.e., patch, gum, lozenge, inhaler, nasal spray), (2)

varenicline, (3) bupropion, and (4) other (fill in).

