(ACT intervention), the mediator M (change from baseline to 3-months post randomization in the acceptance variable, and/or commitment to quitting smoking despite internal cues), and the binary endpoint Y at 12-months post-randomization (e.g., 30-day abstinence). The first regression describes the total intervention effect (X) on the outcome (Y): $\text{logit}(Y) = \gamma_1 + \tau X$, where the parameter τ measures the total intervention effect. The second regression describes the impact of the intervention (X) on the mediator (M): $M = \gamma_2 + \alpha X$. The third regression describes the simultaneous impacts of the intervention (X) and mediator (M) on the outcome (Y): $\text{logit}(Y) = \gamma_3 + \tau'X + \beta M$. Since the endpoint is binary, the mediation effect is the product term $\alpha\beta$, whose empirical distribution will be estimated via 5000 bootstrapped samples. Bootstrapping is a resampling method which provides a powerful test of mediation that does not rely on normality assumptions [93-95]. Randomization should remove potential confounding effects [92, 93], and if needed, we will adjust each model by covariates that differ at baseline or predict outcome. Following VanderWeele and Preacher methods [94, 95], we will also explore any interactions between mediators and treatment arm. And we will explore whether utilization of assigned app and usage of cessation pharmacotherapy mediates cessation outcomes.

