
Exploratory Aim. This aim will explore whether iCanQuit, as compared to QuitGuide, has higher quit rates for those with these baseline factors: (a) those scoring low on acceptance of sensations, emotions, and thoughts that cue smoking, (b) heavy smokers (≥ 20 cigarettes/day), (c) smokers screening positive for mental health symptoms, and (d) being a racial/ethnic minority. **Analyses:** This aim will explore key moderators of ACT treatment outcomes and aid in the critical effort to improve quit rates for these high-risk groups [101-105]. The ACT model suggests that, in addition to being a key mechanism (i.e., mediator) of treatment, baseline acceptance is a moderator of treatment outcome [22]. Specifically, we hypothesize that people who avoid their

triggers to smoke (i.e., low acceptance) will benefit most from ACT because ACT teaches skills to overcome avoidance. We also hypothesize that this focus on acceptance may be especially helpful for heavy smokers and those with mental health symptoms because physical, emotional, and cognitive cues to smoke are stronger for these individuals [106-109]. Finally, testing moderation by race/ethnicity will allow us to generate hypotheses about whether minorities overall respond differently to ACT than non-Hispanic Caucasians. We will explore moderation with separate logistic regression models for each moderator variable, where 30-day abstinence at 12-months post randomization is the outcome (Y). The model will include the moderator (Z), group assignment (X), and an interaction between moderator and group assignment (X*Z). Statistically significant interactions will be assessed with plots showing how the slope of Y on X is dependent on the value of Z. The slopes will be derived from logistic regressions that correspond to the prediction of Y from X at a single value of moderator Z.

Power. We determined sample size with 5,000 iterative simulations aimed at 80% power for Primary Aim 1. We used the following parameters: (1) participants randomized to one of the two arms; (2) two-sided test with $\alpha = .05$; (3) intent-to-treat analysis where, as standard in smoking cessation trials, all those with missing data are coded as smokers [11, 60]. The calculations do not account for potentially higher effect sizes from the adjustment of stratification factors.

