For Primary Aim 1, projected quit rates at 12 month follow-up were conservatively calculated using (1) quit rates at two-month follow-up in our pilot RCT (which used methods similar to this proposed R01) and (2) well-established relapse curves, which provide a data-derived estimate of the rate of decay of 2-month intervention effects by 12 month follow-up [60, 76, 77]. Specifically, the estimates account for a quit rate reduction from the observed two-month 13% quit rate in the pilot to an estimated 11% 12-month quit rate for ACT and from the observed two-month 8% quit rate in the pilot to an estimated 7% 12-month quit rate for QuitGuide. These reduction estimates are consistent with the relapse rates observed by 12 month follow-up [60, 76, 77]. Having 80% two-tailed power to significantly detect a quit rate as low as 11% for iCanQuit (vs. 7% for QuitGuide) required a sample size of 1622. However, we set the target recruitment to 2500 participants for the Exploratory Aim analyses.

For Primary Aim 2, regarding the acceptance mediators, we estimated that they would explain at least 60% of ACT's effect on quitting smoking, as based on prior trials [16, 17, 20, 82]. For the commitment to quitting mediator, we estimated that it would explain at least 25% of ACT's effect on quitting smoking, as based on prior trials [16, 17, 20, 82]. The 5000 iterative simulations showed that a sample size of 811 per arm would provide high power (>99%) to detect the estimated mediation effects for acceptance and commitment.

PROTECTION OF HUMAN SUBJECTS

All procedures for this study will be reviewed by Fred Hutch's IRB prior to human subjects' participation. Based on our prior history with the pilot randomized trial which motivated this proposed trial, we expect no problems obtaining IRB approval.

Experimental design

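### Baseline acceptance (AIS) is tested as a moderator only after a median split, which discards about 36–38% of the information if the score is roughly normal and the interaction is linear

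*Combined protocol and SAP*

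**What the plan says.** The section on moderators of treatment outcome defines the acceptance moderator as "acceptance of cravings to smoke (AIS scores below vs. above the median". The section on ACT mediators describes the AIS as measuring "willingness to experience sensations (9 items), emotions (9 items), and thoughts (9 items) that cue smoking", and Table 4 lists it as "Acceptance of cues (27 items").

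The Exploratory Aim analysis fits "separate logistic regression models for each moderator variable, where 30-day abstinence at 12-months post randomization is the outcome (Y"), with the moderator, the arm and "an interaction between moderator and group assignment (X*Z"). It adds that "Statistically significant interactions will be assessed with plots showing how the slope of Y on X is dependent on the value of Z". That sentence covers all four moderators and does not change the two-level definition of acceptance.

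The hypothesis is directional: people low on acceptance should gain most from ACT. Its rationale proposes no threshold. The Power section says that "we set the target recruitment to 2500 participants for the Exploratory Aim analyses", against the 1622 required for Aim 1. It gives no power calculation for any interaction.

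**The concern.** Cutting a graded score at its sample median treats everyone on one side of the cut as alike and separates people who lie just on either side of it. If the effect of ACT changes gradually with acceptance, as the rationale suggests, the split test uses only part of the information collected.

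The instrument does not force the split. In Aim 2 the plan uses "change from baseline to 3-months post randomization in the acceptance variable" uncut, as the mediator in a linear regression. Nor is there an outside standard for this cut: the depression, anxiety and alcohol screens in the same moderators section have cited cutoffs, while the AIS has only a median that depends on the sample.

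What is at stake is a missed acceptance-by-arm interaction. Of the four moderators, acceptance is the one most closely tied to ACT theory, and the sample was enlarged for the aim that tests it.

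**Working it through.** **Inputs from the documents.** 1:1 allocation; 1,250 per arm; abstinence 7% vs 11%; two-sided alpha 0.05; missing outcomes counted as smoking in the power calculation; 84% retention.

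**Assumptions, because the documents are silent.** AIS distribution (normal first, then other shapes); interaction linear on the logit, of size b log-odds per SD; control-arm slope −0.1 per SD; higher score meaning more acceptance.

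**1. The plan's own figure.** Pooled two-proportion formula with 0.11, 0.07 and mean 0.09:

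n per arm = [1.960·√(2·0.09·0.91) + 0.842·√(0.11·0.89 + 0.07·0.93)]² / 0.04² = 1.133²/0.0016 → 803, or 1,606 in total.

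This is within 3% of 1622, and power at 811 per arm is 80.4%. Aim 1 is therefore covered by 1622, and the further 2500 − 1622 = 878 participants are there for the Exploratory Aim.

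**2. Information kept by a median split, small-effect limit.** Relative efficiency is the squared correlation between the score and its split.

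- Normal: φ(0)²/0.25 = 0.3989²/0.25 = 2/π = 0.637, a loss of 36.3%. Equivalent N: 2500 × 0.637 = about 1,590.
- Uniform: 0.125²/(0.25 × 1/12) = 0.75, a loss of 25%.
- Skewed: gamma with shape 4, loss 41%; gamma with shape 2, loss 45%.
- Heavy-tailed (t with 5 df): loss 46%.

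**3. The planned logistic interaction model.** Large-sample Wald power with sandwich variance, intercepts set to give 7% and 11% overall, normal score, N = 2500:

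| b per SD | Efficiency of split | Power, continuous | Power, split |
|---|---|---|---|
| 0.1 | 0.632 | 11% | 9% |
| 0.2 | 0.629 | 28% | 20% |
| 0.3 | 0.625 | 55% | 38% |
| 0.4 | 0.620 | 79% | 58% |

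The case b = 0.4 is large: the odds ratio between arms is about 2.2 at 1 SD below the mean and about 1.0 at 1 SD above. Varying the control-arm slope from −0.4 to 0.2 gives losses of 36.4–39.4%, mostly 36–38%. In the same model a uniform score gives efficiency 0.74–0.75, and strongly skewed scores give 0.52–0.59.

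**4. Simulation check.** 3,000 trials per cell, normal score, continuous vs split: b = 0.4 at N = 2500, 77.9% vs 57.7%; b = 0.2, 26.8% vs 18.0%; b = 0, 4.6% vs 4.5%. Both codings hold the 5% level.

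**5. Against the enlarged sample.** At b = 0.4, split power rises from about 42% at N = 1622 to 58% at N = 2500, so the extra participants do help. A continuous analysis at N = 1622 already has 60%. To match continuous power at 2500, the split would need 2500/0.620 = about 4,030 participants (2500/0.739 = about 3,380 if uniform).

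**6. Complete cases only.** 2500 × 0.84 = 2,100; 7%/0.84 = 8.3%; 11%/0.84 = 13.1%. Power, continuous vs split: 78% vs 57% at b = 0.4, and 28% vs 19% at b = 0.2.

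**7. If the effect is a step at the median.** The split loses nothing, and continuous coding is the less efficient choice, at about 0.63.

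**The case against.** The split answers the question as the plan words it. The aim asks about people low on acceptance, in order to find subgroups that benefit most, and all four moderators have two levels. A median rule is fixed in advance, rules out a search for a favourable threshold, and yields a group that is easy to report. This stands: the split is an inefficient choice, not an error or a contradiction. But a continuous model also reports the effect at low acceptance, and a displayed split keeps the subgroup estimate.

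The size of the loss depends on facts the documents do not give. With a normal score and small effects, an S-shaped effect Φ(kZ) gives the split an efficiency of 0.79, 0.89 and 0.98 for k = 1, 1.5 and 2. A step at the 40th percentile favours the split slightly (1.07), and a step at the 20th percentile does not (0.51). This also stands, so 36–38% is the figure for one stated scenario. Still, the plan argues for no step near the median.

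Three smaller points are fair. Coding matters little at 0.1–0.2 log-odds per SD, where both tests are weak. The 2500 target serves four moderators and carries no power claim for acceptance, so no promised target is missed. And the moderators section speaks of cravings while the aim names sensations, emotions and thoughts, so either the 27-item total or a 9-item subscale could be meant. The loss is the same for either if the score is roughly normal.

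**Conclusion.** The concern holds, at minor severity. The plan specifies a median split of baseline acceptance, gives no threshold rationale and states no continuous analysis. With a roughly normal score and a linear interaction the loss is about 36–38%. With a linear interaction and the other shapes tried it runs from about 25% to 48%. With a true step at the median it is nil. The practical difference is largest for moderate to large interactions: 55% vs 38% power at 0.3 log-odds per SD, and 79% vs 58% at 0.4. The split does not undo the increase to 2,500, but under these assumptions it costs this one moderator about as much as the 878 extra participants add. The primary analysis is not affected.

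**What to change.** In the Exploratory Aim analysis, enter baseline AIS as a continuous moderator in the logistic model with its arm interaction, and state whether the total or a subscale is used. Pre-specify one check for non-linearity, either a quadratic term or a spline. Report predicted arm differences with 95% confidence intervals at low, middle and high AIS; the planned plots by moderator value suit this. Keep the median split for display only, and say on which side scores equal to the median fall, since the present wording leaves them unassigned.

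The cost is one or two lines of SAP text and no new data. The downside is an assumption of linearity on the logit, which loses efficiency if the true effect is a step. The non-linearity check and the displayed split guard against that.

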Follow-up survey methods. For trial integrity, the follow-up data will be collected by our survey research unit that will be (1) blind to random assignment and (2) collecting cessation outcome data outside of the intervention apps. At each follow-up, we will send reminder letters. Each follow-up survey and Internet tracking will collect address information. The **online-telephone-mailed sequence** data collection protocol is as follows: 1) Three email attempts to complete the online version of the survey; 2) Eight attempts to complete a **telephone** version of survey (one call per day from a trained surveyor); 3) Send a paper version of the survey via **US mail**. Based on our ACT smartphone pilot RCT experience, we conservatively estimate this protocol will yield 84% retention. And to further boost retention, we will make the following protocol enhancements at all follow-up points: (1) mail a \$2 pre-incentive letter (noncontingent incentives increase retention [88]) 2 weeks before the first online survey invitation (i.e., Day -14); (2) provide a \$10 incentive for completing the online survey within 24 hours [89]; and (3) send a postcard with two questions about smoking status.

Table 5. Schedule of key activities.

Year of study	1				2				3				4				5				06 NCE			
Quarter	Q1	Q2	Q3	Q4	Q1	Q2	Q3	Q4	Q1	Q2	Q3	Q4	Q1	Q2	Q3	Q4	Q1	Q2	Q3	Q4	Q1	Q2	Q3	Q4
1. Refinement & Usability	xxx	xxx	xxx	xxx	xxx	xxx																		
2. Set up ^a	xxx	xxx			xxx	xxx	xxx																	
3. Recruitment							xxx	xxx	xxx	xxx	xxx	xxx	xxx	xxx	xx									
4. Interventions							xxx	xxx	xxx	xxx	xxx	xxx	xxx	xxx	xxx	xxx	xxx	xxx	xxx					
5. Outcome Surveys ^b								xx	xxx	xxx	xxx	xxx	xxx	xxx	xxx	xxx	xxx	xxx	xxx	xxx				
6. Data Entry & QC ^c								xxx	xxx	xxx	xxx	xxx	xxx	xxx	xxx	xxx	xxx	xxx	xxx	xxx	xx			
7. Analyses								xxx	xxx	xxx	xxx	xxx	xxx	xxx	xxx	xxx	xxx	xxx	xxx	xxx	xxx	xxx	xxx	xxx
8. Dissemination																						xxx	xxx	xxx

^a Set up study procedures, survey instruments, recruitment materials and advertising; IRB application. ^b3,6,&12 month outcome survey administration protocol (29 days long) timed to participant randomization date. ^cTelephone & mailed versions of each survey are data entered by a trained surveyor. A 20% random sample of entries are checked against audio-recorded telephone surveys and mailed hard copies. Errors over 1% trigger 100% batch re-entry and surveyor performance remediation.

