Analyses. Aim 1. Our primary outcome hypothesis is that iCanQuit will have significantly higher 30-day point prevalence abstinence at 12 months post-randomization than QuitGuide. **Analyses:** For each comparison of the arms on the primary and all secondary endpoints, we will use a logistic regression model with complete case smoking cessation outcome [9-14]. The model will adjust for all stratification factors as well as baseline factors that might be imbalanced after randomization. In addition, we will conduct these analyses: (1) multiple imputation of missing outcomes [90-92], (2) missing equals smoking outcomes [9-14], (3) using a secondary cessation outcome of no use of cigarettes **and** other nicotine or tobacco products except FDA-approved nicotine replacement therapies. Finally, we will compare the two arms on utilization of their assigned app.

Aim 2. We hypothesize that the iCanQuit arm's (but not the QuitGuide arm's) smoking cessation outcomes will be strongly mediated by these psychological measures that are central to the theoretical model underlying ACT: commitment to quitting and acceptance of internal (a) sensations, (b) emotions, and (c) thoughts that cue smoking. This hypothesis is consistent the ACT model and prior ACT for smoking cessation intervention studies [16, 17, 20, 82]. **Analyses:** For each mediator, the model is expressed as three regression equations that relate the main independent variable X

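### Does sizing the trial on missing-equals-smoking leave the complete-case primary analysis without its stated power?

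*Combined protocol and SAP*

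**What the plan says.** The Aim 1 paragraph under Analyses gives one rule for the primary and all secondary endpoints: "we will use a logistic regression model with complete case smoking cessation outcome", adjusted for the stratification factors and for baseline factors that may be imbalanced. It then adds: "In addition, we will conduct these analyses: (1) multiple imputation of missing outcomes [90-92], (2) missing equals smoking outcomes [9-14".

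The Power section lists a different rule among its simulation parameters: "intent-to-treat analysis where, as standard in smoking cessation trials, all those with missing data are coded as smokers". It projects 12-month quit rates by discounting the pilot's two-month rates, "from the observed two-month 13% quit rate in the pilot to an estimated 11% 12-month quit rate for ACT", and from 8% to 7% for QuitGuide. It concludes that 80% two-sided power "required a sample size of 1622". Enrolment was then raised: "we set the target recruitment to 2500 participants for the Exploratory Aim analyses".

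On follow-up, the section on survey methods says "we conservatively estimate this protocol will yield 84% retention", with no figure by arm. The survey unit is "blind to random assignment and (2) collecting cessation outcome data outside of the intervention apps".

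**The concern.** The analysis that was powered is not the analysis that is primary. A complete-case analysis discards the 16% of participants expected to have no outcome, so at first sight 80% power at 1622 becomes 80% power for an analysis with only about 1362 people in it (1622 × 0.84). The Power section also does not state whether 13%/8% and 11%/7% are rates among all randomised or among those who answered. If the primary analysis were short of power, a true difference of the planned size could be missed. With two missing-data rules in the document, a reader might also wonder which result is the headline.

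**Working it through.** **Inputs.** Two-sided alpha 0.05, 11% vs 7%, and 1622 in total (Power section); 811 per arm (same section, Aim 2 paragraph); 2500 in total, 1250 per arm (opening summary); 84% retention (Follow-up survey methods). Equal retention in the two arms is an assumption.

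**Formula.** Two proportions, n per arm, pooled variance under the null, with d = p1 − p2 and m = (p1 + p2)/2:

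power = Φ{ [d − 1.96·√(2m(1 − m)/n)] / √([p1(1 − p1) + p2(1 − p2)]/n) }

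**Step 1: the plan's own figure.** With p1 = 0.11, p2 = 0.07 and m = 0.09, 2m(1 − m) = 0.1638 and the sum of the two variances is 0.0979 + 0.0651 = 0.1630.

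- n = 811: (0.04 − 1.96 × 0.01421)/0.01418 = 0.857, power 80.4%.
- n = 1250: (0.04 − 1.96 × 0.01145)/0.01142 = 1.538, power 93.8%.
- Solving for 80% gives 803 per arm, 1606 in total, within about 1% of 1622.

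The stated figure therefore reproduces with 11% and 7% applied to everyone randomised and no allowance for dropout. An allowance for 16% loss would have given 803/0.84 = 956 per arm, 1912 in total. The calculation was evidently done with rates among all randomised, as its listed missing-data rule says.

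**Step 2: the same assumptions under the complete-case analysis.** If non-responders were counted as smokers to arrive at 11% and 7%, all the quitters are among responders. With 84% responding in each arm:

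- rates: 0.11/0.84 = 13.1% and 0.07/0.84 = 8.33%, difference 4.76 points;
- 2m(1 − m) = 0.1913; sum of variances 0.1138 + 0.0764 = 0.1902;
- n = 811 × 0.84 = 681: (0.0476 − 1.96 × 0.01676)/0.01671 = 0.884, power 81.2%;
- n = 1250 × 0.84 = 1050: (0.0476 − 1.96 × 0.01350)/0.01346 = 1.572, power 94.2%.

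The reason is simple. With retention r, the difference grows by 1/r while n shrinks by r, so the signal d²n changes by 1/r. The variance p(1 − p) becomes (p/r)(1 − p/r), which grows by slightly less than 1/r. The two effects nearly cancel, with a small net gain.

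**Step 3: does it depend on 84%?**

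| Equal retention | Complete-case rates | Power at 1622 | Power at 2500 |
|---|---|---|---|
| 84% | 13.1% vs 8.33% | 81.2% | 94.2% |
| 80% | 13.75% vs 8.75% | 81.4% | 94.3% |
| 70% | 15.7% vs 10.0% | 82.1% | 94.7% |

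Simulating the unadjusted logistic Wald test at 84% agrees: about 80.5% and 93.9% for missing-equals-smoking, 81.2% and 94.3% for complete case. Neither set of figures credits covariate adjustment, and the Power section makes the same reservation about its own.

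**The case for a change.** Three arguments for a change deserve an answer.

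**The denominator is not stated.** If 11% and 7% were rates among responders, complete-case power would be 73.3% at 1622 and 89.4% at 2500. The arithmetic is right. But that reading requires the listed missing-data rule to have been written down and not applied; nothing in the document suggests this, and Step 1 fits the opposite. Even then, the planned enrolment keeps power near 89%.

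**Retention may differ by arm.** True, and then the two rules estimate different things. Take an assumed split of 88% (iCanQuit) and 80% (QuitGuide) at 2500. Complete-case power is 79.5% if 11%/7% hold over all randomised and every non-responder smokes; with the split reversed it is 99.0%. Under no effect (9% in both arms) and the same 8-point gap, complete case errs 11.8% of the time if every non-responder smokes, and missing-equals-smoking errs 10.5% if non-responders quit like responders. Each method, however, holds 5.0% when its own assumption is true, so a gap alone does not inflate error. The gap is hypothetical, and rewording the power paragraph would not remove the bias. What limits it is already planned: blinded follow-up outside the apps, and both alternative analyses, which would show a divergence.

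**Two rules leave room to choose a headline.** The Aim 1 paragraph leaves little. It gives one main model and labels the rest as additional.

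What stands is that the Power section does not mention the primary analysis by name and leaves its denominator implicit.

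**Conclusion.** The inconsistency is one of wording. On the reading the document supports, and with retention equal by arm, the complete-case primary analysis delivers the stated power: 81.2% at 1622 and 94.2% at 2500, against 80.4% and 93.8% for the analysis used in sizing. The 2500 planned already exceeds the calculated need. The primary rule is named, and the rule used for sizing will itself be run as an additional analysis.

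Rewriting the sizing assumption would bring no gain and could do harm. It is the record of how 1622 was obtained; substituting complete case at 84% retention while leaving 11% and 7% untouched would produce text that implies 73% power at 1622. A reader can supply the missing link from the calculation above. No change to the plan follows.

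This rests on equal retention by arm, which the document does not give, and on 11%/7% being rates among all randomised, which it implies but does not spell out.

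### Minor: the primary Aim 1 model adds covariates that happen to look imbalanced, under no stated cut-off; fix a short prognostic list before outcomes are seen

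*Combined protocol and SAP*

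**What the plan says.** The Aim 1 paragraph under Analyses specifies a complete-case logistic regression for the primary endpoint (30-day point prevalence abstinence at 12 months) and for all secondary endpoints. On covariates it states: "The model will adjust for all stratification factors as well as baseline factors that might be imbalanced after randomization".

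The stratification factors are named consistently in two places, the randomized trial experimental design paragraph and the Experimental design section under Protection of Human Subjects. They are daily smoking frequency, education, race/ethnicity and the CES-D depression screen. The additional baseline factors are named nowhere.

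For the Aim 2 mediation regressions the plan uses a different open rule: "if needed, we will adjust each model by covariates that differ at baseline or predict outcome".

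The Power section codes all participants with missing outcomes as smokers and says of covariates: "The calculations do not account for potentially higher effect sizes from the adjustment of stratification factors". On that basis 80% power for 11% versus 7% "required a sample size of 1622", but "we set the target recruitment to 2500 participants for the Exploratory Aim analyses". The follow-up section says of retention: "we conservatively estimate this protocol will yield 84% retention". Missing-equals-smoking appears in the Aim 1 paragraph as an additional analysis.

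**The concern.** The covariate set of the primary model is settled by the data. Three things are left open: which baseline measures are candidates, what counts as imbalanced (a test, a p-value or a standardized difference), and whether the choice is made before outcomes by arm are seen. Blinding is stated for the survey unit that collects outcomes; nothing comparable is stated for covariate selection.

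The candidate pool is large. Table 4 appears to list 17 baseline measures with 160 items. That count is approximate: part of the table lost its column headings in text extraction, and the Survey Data section also mentions commitment to quitting and readiness to quit, which have no row of their own. With so many candidates, some will look imbalanced by chance in most trials.

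Chance imbalance is also a poor selection rule. A variable that differs between arms but does not predict abstinence needs no adjustment, and a strong predictor is worth including even when balanced. At stake is the credibility of a definitive efficacy result close to the significance threshold, where an unstated cut-off could decide the conclusion.

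**Working it through.** **1. Is the rule closed elsewhere?** The Aim 1, Aim 2, Power, Table 4 and follow-up sections give no list, threshold or timing for the extra Aim 1 covariates. The rule is open.

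**2. How often would it act?** Assume 15 candidate scores: the 17 Table 4 rows less depression and tobacco use, treated as carrying stratification factors. If the scores were independent, the chance that at least one passes an imbalance test at level c is 1 − (1 − c)^15: 54% at c = 0.05, 79% at 0.10 and 96% at 0.20. With an assumed pairwise correlation of 0.2, simulation gives 50%, 76% and 95%.

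**3. What does it do to the test?** Simulation inputs from the plan: 1250 per arm, 84% retention, four balanced binary stratification factors, logistic Wald test at two-sided 0.05. Assumed inputs: response missing at random, and covariate strength. Strong means an odds ratio of 0.70 per SD for nicotine dependence, 0.85 for five other scores, and nine null scores. Weak replaces these odds ratios by 0.85 and 0.95.

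| No true effect, 4000 replicates | Strong | Weak |
|---|---|---|
| Two-sided error, stratification factors only | 4.60% | 5.35% |
| Fixed prognostic list | 4.75% | 5.20% |
| Imbalance p<0.05 | 4.65% | 5.28% |
| Imbalance p<0.10 | 4.60% | 5.28% |
| Imbalance p<0.20 | 4.58% | 5.32% |
| Favourable false positives, stratification factors only | 2.22% | 2.58% |
| Favourable false positives, best pick from p<0.10 pool | 2.88% | 2.92% |
| Favourable false positives, best pick from p<0.20 pool | 3.20% | 3.10% |

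Monte Carlo standard error is 0.34 points for the two-sided rows and 0.25 for the favourable rows.

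Two further simulations on other assumed inputs agree in direction. Reporting the best of four models gave about 3.3% favourable false positives against 2.2%. With 20 covariates, two-sided error was 5.1% with stratification factors only, 4.9-5.1% at each fixed cut-off, 5.45% with a fixed list, and 6.1% for the best of four models (simulation error about 0.35 points).

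**4. How often do the three cut-offs disagree on significance?** Under no effect, 0.7-1.7% of trials. At the planned effect (13.1% versus 8.3% among respondents, strong covariates), 1.7%. At half that effect (10.7% versus 8.3%), 2.4-5.7%. Among trials whose stratification-only p lies between 0.02 and 0.10, 9-21%.

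**5. Does a fixed list cost power?** At the planned effect it has 95.2% power, against 94.7-95.1% for the alternatives (standard error 0.5): no loss and no material gain. These runs had no missing baseline scores.

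**6. Power in the plan.** Pooled two-proportion formula:

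n per arm = [1.960·√(2·0.09·0.91) + 0.842·√(0.11·0.89 + 0.07·0.93)]² / 0.04² ≈ 803, or 1606 in total. This is 1.0% below the plan's simulated 1622. Power is 80.4% at 811 per arm and 93.8% at 1250 per arm.

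For complete case, 0.84 × 1250 = 1050 per arm are analysed. If 11% and 7% are rates among all randomised and retention is equal, respondent rates are 0.11/0.84 = 13.1% and 0.07/0.84 = 8.3%, and power is 94.2%. If 11% and 7% are respondent rates, power is 89.4%.

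**The case against.** The best defence is that the rule does little damage. The trigger is baseline imbalance, which uses no outcome data, and the core of the model is fixed by the stratification factors. Each mechanical cut-off holds its error rate, and a fixed list gains no appreciable power. The rise in favourable false positives assumes a deliberate search, which the plan does not describe; it is modest against a nominal 2.5%, and some comparators (2.2%) lie below nominal. The 9-21% disagreement applies only to trials already near the threshold. All of this stands, and it makes the point minor.

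The choice of 15 candidates is also open to challenge. Demographics, which plausibly carries education and race/ethnicity, stayed in the pool, as did nicotine dependence, which Table 4 tags for stratification. Removing both moved half-effect disagreement from 4.7% to 3.8% (1500 replicates, standard error about 0.5). The conclusion does not change.

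Three stronger readings are tempting, and the documents do not support them:
- **The imbalance rule itself inflates type I error.** It does not when one cut-off is applied mechanically.
- **The trial is underpowered because the power basis and the primary analysis treat missing outcomes differently.** At the 2500 target, complete-case power is 89.4% or 94.2% at 84% retention. The missing wording is a reporting gap.
- **The open Aim 2 rule undermines the mediation test through the total-effect regression.** That test is the product of the intervention-to-mediator and mediator-to-outcome coefficients; the total effect does not enter it.

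**Conclusion.** The point holds as a minor improvement. The primary model's extra covariates depend on chance imbalance under an unstated cut-off, and nothing requires the choice to precede sight of outcomes by arm. That is a textual fact and needs no simulation.

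Its size is small and comes only from discretion: favourable false positives of about 2.9-3.3% instead of 2.2-2.6%, and disagreement between cut-offs in about 1-6% of trials. These figures rest on assumed candidate numbers, correlations and covariate strengths, which the documents do not give, and on missing-at-random response. No stated sample size or power figure has to change.

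**What to change.** In the Aim 1 analysis paragraph, replace the imbalance rule with a list fixed before outcomes by arm are seen and entered regardless of imbalance. The list is the four stratification factors, written out by name, plus one or a few named prognostic baseline measures already collected. The baseline nicotine dependence score is a candidate: Table 4 gives its purpose as stratification and Aim 1, but it is not one of the four factors. Adjustment for any other imbalanced variable becomes a labelled sensitivity analysis.

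Name the covariates for all the Aim 2 regressions in advance as well, with the same set in the total-effect and direct-effect models, so that those two coefficients stay comparable.

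The cost is a few sentences, with no new data and no new participants. There are two downsides. Imbalance in an unlisted variable is addressed only in the sensitivity analysis. And because the section on protection against emotional upset lets participants skip items, a listed score may be missing; a simple stated rule for a missing baseline score is needed so that nobody drops out of the primary model.

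Optional reporting notes: add one sentence giving complete-case power at 2500 and saying whether 11% and 7% are rates among all randomised or among respondents. Correct the purpose labels in Table 4, where nicotine dependence and quitting self-efficacy are tagged for stratification and depression is not.
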